6.8.4 Prohibited Food

Use of the following foods is prohibited during the study and for at least 7 days prior to initiation of study treatment: furanocoumarin derivatives, such as those found in grapefruit, Seville oranges, pomegranates, or star fruit juice or products.

6.8.5 Immunizations

Participants will be excluded from study participation if they have been vaccinated with a live or live-attenuated vaccine (e.g., the intranasal live attenuated influenza vaccines, bacille Calmette Guérin, varicella) within 6 weeks of randomization. In addition, immunization with a live or live-attenuated vaccine is prohibited for the duration of study participation, including the SFU phases.

The effect of fenebrutinib upon the efficacy of vaccinations is unknown. Vaccinations with vaccines other than live or live-attenuated vaccinations are permitted during the study period. It is recommended that all vaccinations, other than live or live-attenuated vaccinations, should follow the local immunization schedule. In addition, measurement of vaccine-induced response titers should be considered to determine if individuals can mount a protective immune response as the efficacy of the vaccination may be decreased. Administration of a seasonal influenza vaccine, except for the intranasal live-attenuated influenza vaccine, is recommended but not required.

Refer to Fenebrutinib Investigator’s Brochure and [Appendix A6-1.4](#) for further details and precautions regarding vaccinations.

7. DISCONTINUATION OF STUDY TREATMENT AND PARTICIPANT DISCONTINUATION OR WITHDRAWAL

7.1 DISCONTINUATION OF STUDY TREATMENT

It may be necessary for a participant to permanently discontinue (definitive discontinuation) study treatment. If study treatment is definitively discontinued, the participant should move to the Safety Follow-up Period. Refer to the schedule of activities (see Section 1.3) for data to be collected at the time of discontinuation of study treatment (“Early Discontinuation Visit”) and the further follow-up evaluations that need to be completed in the Safety Follow-up Period.

Participants must permanently discontinue study treatment if they experience any of the following:

- Any medical condition that the investigator or Sponsor determines may jeopardize the participant's safety if he or she continues to receive study treatment
- Investigator or Sponsor determination that treatment discontinuation is in the best interest of the participant
- Demonstrate active hepatitis B infection
- PML
- First observation of AST or ALT elevation $> 8 \times$ ULN
- AST or ALT elevation $> 5 \times$ ULN persisting more than 2 weeks
- AST or ALT elevation $> 3 \times$ ULN in combination with any of the following:
 - Total bilirubin $> 2 \times$ ULN or clinical jaundice as defined by Hy’s Law
 - INR > 1.5
 - Symptoms of hepatitis, such as fatigue, nausea, vomiting, right upper quadrant pain or tenderness
 - Signs or symptoms of immune-related hepatotoxicity (fever, rash, or eosinophilia $> 5\%$)
- *ALT or AST elevation between $3\text{--}5 \times$ ULN (inclusive) persisting for 4 weeks and in absence of alternative etiology*
- Grade 3 neutropenia (ANC $500\text{--}1000/\text{mm}^3$) persisting more than 1 month or reoccurring
- Grade 4 neutropenia (ANC $< 500/\text{mm}^3$)
- Grade 2 thrombocytopenia (platelet count $50,000\text{--}75,000/\text{mm}^3$) persisting more than one month or reoccurring
- Grade 3 thrombocytopenia (platelet count $25,000\text{--}50,000/\text{mm}^3$) or Grade 4 thrombocytopenia ($< 25,000/\text{mm}^3$)
- Malignancy (with the exception of non-serious local and resectable basal or squamous cell carcinoma of the skin)

- Pregnancy
- An episode of torsade de pointes or a new ECG finding of clinical concern or sustained (at least two ECG measurements > 30 minutes apart) QTcF that is > 500 ms and/or > 60 ms longer than the baseline value (unless there is a clear alternative cause other than study drug) as described in [Appendix 6](#). Electrocardiogram assessment should be conducted as outlined in [Section 8.2.3](#).
- Requirement of *chronic use* of any prohibited medication as defined in [Section 6.8.3](#). *If any prohibited medication is considered to be medically necessary, the investigator should discuss with the Medical Monitor.*

The primary reason for study treatment discontinuation should be documented on the appropriate eCRF.

Refer to the schedule of activities in [Section 1.3](#) (see [Table 1](#)) for details on follow-up assessments to be performed for participants who permanently discontinue study treatment. If a participant requests to be withdrawn from treatment or follow-up assessments, this request must be documented in the source documents and signed by the investigator.

7.2 PARTICIPANT DISCONTINUATION OR WITHDRAWAL FROM THE STUDY

A participant may withdraw from the study at any time at his or her own request, or may be withdrawn at any time at the discretion of the investigator for safety, behavioral, compliance, or administrative reasons.

The primary reason for discontinuation from the study should be documented on the appropriate eCRF. If a participant requests to be withdrawn from the study, this request must be documented in the source documents and signed by the investigator.

At the time of discontinuing from the study, if possible, an early discontinuation visit should be conducted, as shown in the schedule of activities (see [Section 1.3](#)). Refer to the schedule of activities for data to be collected at the time of study discontinuation and follow-up and for any further evaluations that need to be completed.

The participant will be permanently discontinued both from the study treatment and from the study at that time.

If a participant withdraws consent from the study, the Sponsor may retain and continue to use any data collected before withdrawal of consent. Samples collected prior to withdrawal may be analyzed, unless the participant specifically requests that the samples be destroyed (as documented in the source documents) or local laws require destruction of the samples. However, if samples have been tested prior to withdrawal, results from those tests will remain as part of the overall research data.

7.3 PARTICIPANTS LOST TO FOLLOW-UP

A participant will be considered lost to follow-up if he or she repeatedly fails to return for scheduled visits and is unable to be contacted by the study site.

The following actions must be taken if a participant fails to return to the clinic for a required study visit:

- The site must attempt to contact the participant and reschedule the missed visit as soon as possible and counsel the participant on the importance of maintaining the assigned visit schedule. If the participant is unable or unwilling to comply with study visits, site personnel should assess reasons the participant is unable or unwilling to return to the clinic, and determine if there are ways to support participant participation.
- Before a participant is deemed lost to follow-up, the investigator or designee must make every effort to regain contact with the participant (where possible, three telephone calls and, if necessary, a certified letter to the participant's last known mailing address or local equivalent methods). These contact attempts should be documented in the participant's medical record.
- Should the participant continue to be unreachable, he or she will be considered lost to follow-up and will be withdrawn from the study.

Discontinuation of specific sites or of the study as a whole are handled as part of [Appendix 1](#).

8. STUDY ASSESSMENTS AND PROCEDURES

Written informed consent for participation in the study must be obtained before performing any study-related procedures (including screening evaluations). Informed Consent Forms for enrolled individuals and for individuals who are not subsequently enrolled will be maintained at the study site.

Study procedures and their timing are summarized in the schedule of activities (see Section 1.3). Protocol waivers or exemptions are not allowed.

Immediate safety concerns should be discussed with the Sponsor immediately upon occurrence or awareness to determine if the participant should continue or discontinue study treatment.

Adherence to the study design requirements, including those specified in the schedule of activities, is essential and required for study conduct.

All screening evaluations must be completed and reviewed to confirm that potential participants meet all eligibility criteria. The investigator will maintain a *detailed* record of all participants screened and to *document* eligibility or record reasons for screening failure, as applicable.

Medical history and baseline conditions, including clinically significant diseases, surgeries, cancer history (including prior cancer therapies and procedures), and reproductive status will be recorded at baseline. Previous treatment with anti-CD20 therapy (e.g., rituximab, ocrelizumab) should be reported up to 3 years prior to randomization and other MS DMTs should be reported up to 1 year prior to randomization. Receipt of any prior SARS-CoV-2 vaccine should be recorded in the concomitant medications eCRF. All other medications (e.g., prescription drugs, MS symptomatic therapies, over-the-counter drugs, vaccines, herbal or homeopathic remedies, nutritional supplements) and non-medicinal treatments (e.g., physiotherapy, occupational therapy) used by the patient within 3 months prior to initiation of study treatment will be recorded in the appropriate eCRF. Demographic data, including age, sex, and self-reported race/ethnicity, will also be recorded if allowed per local regulations. At the time of each follow-up physical examination, an interval medical history should be obtained and any changes in medications and allergies should be recorded.

Participants will be closely monitored for safety throughout the study. Participants should be assessed for toxicity prior to each dose; treatment will be administered only if the clinical assessment and local laboratory test values are acceptable. Urgent safety concerns should be discussed with the Sponsor immediately upon occurrence or awareness to determine if the participant should continue or discontinue study treatment.

8.1 EFFICACY ASSESSMENTS

8.1.1 Magnetic Resonance Imaging

Magnetic resonance imaging (MRI) is a useful tool for monitoring CNS lesions in MS. Different MRI derived parameters have been related to clinical activity and T1 weighted Gd-enhancing lesions or new and/or enlarging hyperintense T2 lesions have been related to relapses.

Radiologic evaluation for the primary efficacy parameter will be performed using a standardized MRI protocol at screening, and at Weeks 4, 8, and 12. Measurements from the screening MRI scan sequences will be used for the baseline MRI measurements; therefore, these sequences do not need to be repeated at the baseline visit. In addition, mandatory MRI scans will be obtained in participants who withdraw from study treatment (at withdrawal visit) if one was not performed during the prior 4 weeks. *While MRI scans are acquired in this study to support the primary and secondary endpoints, the set of images from each examination allows for the possibility of additional exploratory measurements.*

All MRI scans will be read by a centralized reading center for efficacy endpoints. The centralized reading center will be blinded to treatment assignment, and the reading will be performed in the absence of clinical information. Further details on scanning acquisition sequences, methods, handling, and transmission of the scans, certification of

site MRI radiologist/technicians, and the procedures for the blinded analysis of the scans at the central reading center will be described in separate MRI acquisition procedures manuals *and Imaging Review Charters*.

All MRI scans will also be reviewed locally by a radiologist for safety, and a MRI scan report containing only non-MS pathology will be provided to the treating investigator. During the DBT phase, only the local radiologist/technician at the investigational site who is assigned to this study may have access to the MRI scans, except at screening when the treating investigator may view the MRI scan. To maintain the blind, the treating investigator must not review the MRI scans obtained after randomization unless a safety concern arises. In the event that the treating investigator becomes aware of these MRI results, this should be documented in the eCRF, indicating the reason. The treating investigator may have access to MRI scans performed during the OLE phase *from their MRI facility*.

If participants receive corticosteroids for an MS relapse, every effort should be made to obtain an MRI scan prior to the first corticosteroid dose if the pre-corticosteroid scan is within 1 week of the scheduled visit. In participants receiving corticosteroids for an MS relapse, there should be an interval of 3 weeks between the last dose of corticosteroids and the MRI scan.

8.1.2 Clinical Outcome Assessments

Disability will be measured using the EDSS. The EDSS is based on a standardized neurological examination, incorporating functional systems (visual, brainstem, pyramidal, cerebellar, sensory, bowel and bladder, and cerebral [or mental]) that are rated and then scored as a functional systems score (FSS), and ambulation, which is scored as ambulation score. Each FSS is an ordinal clinical rating scale ranging from 0 to 5 or 6 and an ambulation score that is rated from 0 to 16. These ratings are then used in conjunction with observations, as well as information, concerning ambulation and use of assistive devices to determine the total EDSS score. The EDSS is a disability scale that ranges in 0.5-point steps from 0 (normal) to 10.0 (death) (Kurtzke 1983; Kappos 2011). All FSS, ambulation score, and total EDSS scores will be captured electronically. Note that the following items do not need to be scored for this study: sexual dysfunction and fatigue.

8.1.3 MS Relapse Assessment

All new or worsening neurological events compatible with MS representing a clinical relapse will be reported in the appropriate eCRF. The EDSS/FSS evaluation can be performed by the Principal Investigator or by a designated sub-investigator. Whenever possible, the same rater should evaluate a patient throughout the study. The EDSS should be performed within 7 days from the onset of the relapse. If the change or intensification of existing neurological symptoms are more likely attributed to a transient systemic infection, then a referral to the examining investigator may not be warranted.

For this study, a protocol-defined relapse is defined as the occurrence of new or worsening neurological symptoms attributed to MS and immediately preceded by a relatively stable or improving neurological state of at least 30 days. Symptoms must persist for >24 hours and should not be attributable to confounding clinical factors (e.g., fever, infection, injury, adverse reactions to concomitant medications). The new or worsening neurological symptoms must be accompanied by objective neurological worsening consistent with an increase of at least one of the following:

- Half a step (0.5 point) on the EDSS
- Two points on one of the selected FSS listed below
- One point on two or more of the selected FSS listed below

The change must affect the following selected FSS: pyramidal, ambulation, cerebellar, brainstem, sensory, or visual. Episodic spasms, sexual dysfunction, fatigue, mood change, or bladder or bowel urgency or incontinence will not suffice to establish a relapse. Note that the following items need not be scored: sexual dysfunction and fatigue.

Derivation of protocol-defined relapses will be performed by the Sponsor. Clinical relapses (i.e., regardless of whether or not they meet the criteria for a protocol-defined relapse) will be recorded in the eCRF.

8.2 SAFETY ASSESSMENTS

8.2.1 Physical Examinations

A complete physical examination will include, at a minimum, assessments of the head, eyes, ears, nose, and throat and evaluation of the cardiovascular, dermatologic, musculoskeletal, respiratory, and gastrointestinal systems; genitourinary examinations may be performed if clinically indicated. Any abnormality identified at baseline should be recorded on the General Medical History and Baseline Conditions eCRF. A neurological examination includes, but is not limited to, an assessment of mental status, level of consciousness, cranial nerve function, motor function, sensory function, reflexes, and coordination. During an unscheduled visit, the neurological examination must be performed if the patient is experiencing neurological worsening between scheduled visits.

8.2.2 Vital Signs

Vital signs will be measured in a seated position after 5 minutes rest and will include temperature, systolic and diastolic blood pressure, pulse, and respiratory rate.

8.2.3 Electrocardiograms

Single 12-lead ECGs will be obtained as outlined in the schedule of activities (see Section 1.3) using an ECG machine that automatically calculates the heart rate and measures PR interval, QRS interval, and QT interval. QT interval corrected through use of Fridericia's formula (QTcF) can be calculated by the ECG machine or using standard

formulas. Refer to [Appendix 6](#) for QTc withdrawal criteria and any additional QTc readings that may be necessary.

Lead placement should be as consistent as possible. ECG recordings must be performed after the participant has been resting in a supine position for at least 10 minutes. All ECGs are to be obtained prior to other procedures scheduled at that same time (e.g., vital sign measurements, blood draws). Circumstances that may induce changes in heart rate, including environmental distractions (e.g., television, radio, conversation) should be avoided during the pre-ECG resting period and during ECG recording.

For safety monitoring purposes, the investigator must review, sign, and date all ECG reports. Paper copies of ECG tracings will be kept as part of the participant's permanent study file at the site. The following should be recorded on the appropriate eCRF: heart rate, RR interval, QRS interval, PR duration, uncorrected QT interval, and QTcF based on machine readings of the individual ECG tracings. Any morphologic waveform changes or other ECG abnormalities must be documented on the eCRF. If considered appropriate by the Sponsor, ECGs may be analyzed retrospectively at a central laboratory.

If at a particular postdose timepoint the mean QTcF is > 500 ms and/or > 60 ms longer than the baseline value, another ECG must be recorded, ideally within the next 5 minutes, and ECG monitoring should continue until QTcF has stabilized on two successive ECGs. The Medical Monitor should be notified. Standard-of-care treatment may be instituted at the investigator's discretion. If a PK sample is not scheduled for that timepoint, a PK sample should be obtained. A decision on study drug discontinuation should be made, as described in [Appendix 6](#) (Section [A6-2.4](#)). The investigator should also evaluate the participant for potential concurrent risk factors (e.g., electrolyte abnormalities, co-medications known to prolong the QT interval, severe bradycardia).

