- ^d Participants who discontinue from the study prior to completion should be encouraged to return to the clinic for an Early D/C visit. If a patient states intention to discontinue participation at the Week 4, Week 8, or an UV prior to Week 12, that visit should be converted to an Early D/C Visit.
- ^e A Safety Follow-up Visit should be performed in 2 situations: 1) 4 weeks after early discontinuation of study drug, or 2) for participants that complete the double-blind treatment period (Week 12) who do not elect to participate in the OLE, in which the visit should be performed at Week 16.
- ^f Informed consent must be documented before any study-specific screening procedure is performed.
- ^g Includes respiratory rate, pulse rate, and systolic and diastolic blood pressure while the participant is in a seated position, and temperature. Temperature should be noted in the participant's notes only.
- ^h Includes an evaluation of the head, eyes, ears, nose, and throat and evaluation of the cardiovascular, dermatologic, musculoskeletal, respiratory, gastrointestinal, and neurological systems; genitourinary examinations may be performed if clinically indicated.
- ⁱ A separate neurological examination should be performed by the treating physician if the treating physician is not performing the EDSS. During an UV, the neurological examination must be performed if the participant is experiencing neurological worsening between scheduled visits.
- ^j The EDSS can be performed by either the treating investigator or a separate examining investigator. The person performing the EDSS must have a valid Level C Neurostatus certification.
- ^k ECG recordings must be performed after the participant has been resting in a supine position for at least 10 minutes.
- ^l Participants should fast prior to the blood draws for Visits 2, 3, 4, and 5.
- ^m Flow cytometry: Analysis may include, but is not limited to, the determination of B-cell and T-cell numbers and other lymphocyte subsets.
- ⁿ *Biomarker and RBR samples should be collected prior to the administration of study drug (predose).*

Table 1 Schedule of Activities (cont.)

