- ^s Semi-structured telephone interviews will be conducted every 6 weeks (± 3 days) between study visits (when there are dates overlapping with site visits, telephone calls will not occur). Please see [Appendix 10](#) for more details. If the participant answers YES to any question during the semi-structured telephone interview, the answer should be discussed and reviewed by the investigator. If warranted, the participant should return for an UV. If an unplanned pregnancy is suspected, an UV to confirm the pregnancy is required.

Table 3 Schedule of Pharmacokinetic Samples for Double-Blind Treatment

Visit	Timepoint	Sample Type
Day 1 (Week 0) and 29 (Week 4)	Prior to the morning dose, fasted ^a	PK (plasma)
	1–2 hours after dosing, fasted	PK (plasma)
Day 1 (Week 0) and Day 29 (Week 4) (if applicable) ^b	Prior to the morning dose, fasted ^a	PK (plasma)
	1 hour (\pm 10 minutes) after dosing, fasted	PK (plasma)
	2 hours (\pm 10 minutes) after dosing, fasted	PK (plasma)
	4, 6, and 8 hours (\pm 10 minutes) after dosing ^c	PK (plasma)
Day 57 (Week 8)	Predose ^a	PK (plasma)
Day 85 (Week 12)	Predose ^a	PK (plasma)
Unscheduled visit ^d	NA	PK (plasma)
Early D/C visit	NA	PK (plasma)

D/C = discontinuation; NA=not applicable; PK=pharmacokinetic; PPI=proton pump inhibitor.

Notes:

Morning clinic visits are preferred for all visits but are required on Days 1, 15, and 29. Prior to each morning clinic visit, participants should be instructed not to take their morning dose and to bring their study medication with them to their clinic visit. The dates and times of the most recent prior meal, last dose of oral study drug (prior to the clinic visit), and timing of oral study drug administration in the clinic should be recorded at each clinic visit. Use of PPIs, H₂-receptor antagonists, and/or other antacids (e.g., bismuth subsalicylate, calcium carbonate, aluminum-magnesium hydroxide) should be recorded as concomitant medications, including the date and time of last administration at each clinic visit.

Single-dose acid-reducing agents are not permitted on the day of an in-clinic visit with PK assessments.

- ^a Participants should be fasting for >6 hours overnight prior to the sample collection, which must be performed at the clinic in the morning. The PK samples should be collected 5–30 minutes prior to the fenebrutinib dose.
- ^b For participants participating in the intensive PK sample collection only.
- ^c Fasting is not required for these samples.

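### ECG timing relative to dose is not set: the plan favours trough recording and requires no ECG 1–2 h after dosing, yet Section 8.2.3 has a post-dose QTcF rule

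*Protocol*

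**What the plan says.** Protocol Section 8.2.3 specifies the recordings: "Single 12-lead ECGs will be obtained as outlined in the schedule of activities". That schedule (Section 1.3, Table 1) has ECGs at screening, Weeks 0, 4 and 12, and early discontinuation. The only ECG footnote concerns rest: "ECG recordings must be performed after the participant has been resting in a supine position for at least 10 minutes". Section 8.2.3 adds an ordering rule: "All ECGs are to be obtained prior to other procedures scheduled at that same time (e.g., vital sign measurements, blood draws".

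Dosing and PK sampling are timed in Table 3. Its notes say: "Prior to each morning clinic visit, participants should be instructed not to take their morning dose". Its first footnote times the predose draw: "The PK samples should be collected 5–30 minutes prior to the fenebrutinib dose". At Weeks 0 and 4 every participant also has a draw "1–2 hours after dosing, fasted".

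Section 8.2.3 then gives an action rule that begins: "If at a particular postdose timepoint the mean QTcF is > 500 ms and/or > 60 ms longer than the baseline value".

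Protocol Section 9.4.5 and SAP Section 5.6 display ECG data by time and summarise changes. Protocol Section 9.4.6.2 defines baseline as the last data before study treatment starts.

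**The concern.** The post-dose QTcF rule presupposes something that the schedule does not provide. No ECG is assigned a post-dose time, and a single tracing gives no mean. The instructions that do exist pull the on-treatment ECGs towards the moment just before the morning dose, when drug concentration is at its lowest in the dosing interval.

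ECG is one of the standard safety measures named in Section 4.2.5, and QTcF above 60 ms over baseline is one of the discontinuation criteria in Section 7.1. Appendix A6-1.8 says that cardiac safety will be followed, with routine safety ECGs among the measures, until ECG effects can be ruled out. If the tracings are all at trough, or a site-dependent mix of trough and post-dose, an unremarkable summary of ECG changes says less about the drug at higher concentrations than a reader of the study report would assume.

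**Working it through.** No sample-size or power figure bears on this, so the check is a cross-reading of Table 1, Table 3 and Section 8.2.3.

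**Step 1. ECG visits against PK draws, double-blind phase after screening.**

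| Visit | ECG (Table 1) | Main-study PK draw (Table 3) | ECG time relative to dose |
|---|---|---|---|
| Week 0 | yes | predose and 1–2 h post-dose | not stated |
| Week 4 | yes | predose and 1–2 h post-dose | not stated |
| Week 8 | no | predose | – |
| Week 12 | yes | predose only | not stated |
| Early discontinuation | yes | no set timepoint | not stated |

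ECGs labelled predose: 0. ECGs required in the 1–2 h window: 0. ECG visits that also have a 1–2 h draw for everyone: 2 (Weeks 0 and 4), of which only Week 4 falls during repeated dosing. Week 12 sampling at 1–2 h exists only in the optional CSF substudy of about 10 participants (Table 8, Section 4.2.8).

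**Step 2. The ordering rule, read both ways.**

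- If the same time means the visit, the ECG precedes all blood draws. The first draw is 5–30 minutes before a dose held until clinic, so the ECGs at Weeks 0, 4 and 12 are all predose.
- If it means a nominal timepoint, Week 12 still points to predose, since its only main-study PK draw is predose. At Week 4 an ECG before either draw complies, so timing is left to the site. Week 0 is then open too. An ECG taken before the 1–2 h draw would follow the first dose and could not serve as baseline under Section 9.4.6.2.

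Predose recording is therefore likely at Week 12 and favoured at Week 4. Under the second reading the Week 4 summary may mix the two kinds of tracing. The ECG items that Section 8.2.3 lists for the eCRF do not include the time of the tracing, so the documents do not show that the two kinds could be separated afterwards.

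**Step 3. The action rule against the schedule.** The rule needs a post-dose timepoint and a mean QTcF. Table 1 schedules no ECG at a stated time after a dose, and Section 8.2.3 specifies single recordings. The repeat ECG, ideally within 5 minutes, is a consequence of the trigger and cannot supply the mean that triggers it.

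**Step 4. Count.** With 68 participants planned on fenebrutinib and 34 on placebo (Section 9.2), Weeks 4 and 12 give at most 68 × 2 = 136 and 34 × 2 = 68 scheduled on-treatment ECGs before dropout. Half of each (68 and 34) are the Week 4 tracings that could be placed after the dose.

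**Step 5. What lies outside that count.** Early-discontinuation ECGs have no fixed relation to dose. In the extension (Table 2), ECGs fall at its baseline (the double-blind Week 12 visit), Weeks 4, 12 and 48, every 24 weeks after that, and early discontinuation. Extension Week 4 has an ECG but no PK sample, and the held-dose instruction belongs to the double-blind table.

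**The case against.** The strongest reply is that the ordering rule never mentions dose. It fixes sequence within a timepoint, and an ECG just before the 1–2 h draw at Week 4 would comply. This stands. A reader might infer that every on-treatment ECG is predose, or that the trial takes no ECG after dosing. The documents support only that none is required in that window and that predose recording is favoured.

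Second, the discontinuation criteria in Section 7.1 and Appendix A6-2.4 apply to any sustained QTcF finding, with no post-dose qualifier. The word postdose in 8.2.3 could also mean any time after treatment began, in which case the Week 4 and Week 12 ECGs qualify. Both points are fair: the safety rules do not lapse without a timed ECG. The ambiguity itself and the conflict between single and mean remain.

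Third, Appendix A6-1.8 states a low potential for QT prolongation and reports no significant QRS or QTcF increase in the single- and multiple-ascending dose studies. ECG change is not among the Table 5 safety endpoints, and a small concentration-related effect is not a stated target. This lowers the expected consequence. The same appendix nevertheless keeps ECG evaluation going until effects can be ruled out, and the Phase I data are from healthy participants.

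Fourth, a reader might put a size on the effect missed at trough. With mono-exponential decline, the fraction remaining from 1.5 h to 12 h is 0.5^(10.5/half-life): 0.16 for an assumed half-life of 4 h and 0.55 for 12 h. The documents give no half-life, peak time or concentration–QTc slope, and intensive sampling runs to 8 h, so even equating 1–2 h with peak exposure is an assumption. No attenuation figure can be claimed.

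**Conclusion.** The point holds as a gap in timing and an internal mismatch. No section sets ECG timing relative to dose. Followed as written, the plan probably yields trough ECGs at Week 12 and either trough or mixed ECGs at Week 4. The double-blind phase requires no ECG in the 1–2 h post-dose window, while Section 8.2.3 has a rule that refers to a post-dose timepoint and a mean QTcF alongside single recordings. Early-discontinuation and extension ECG timing is also open.

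The size is two scheduled ECGs per participant, up to 136 on fenebrutinib. The trough conclusion assumes that sites apply the ordering rule to the PK draws and that participants hold the dose as instructed. The clinical consequence is probably modest given the stated QT profile, and its magnitude cannot be derived. The change is worth making because it is cheap and makes the existing ECGs more informative.

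**What to change.** In Table 1 and Section 8.2.3:

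- Label the Week 0 ECG predose, as the QTcF baseline.
- Place the existing Week 4 ECG just before the 1–2 h post-dose PK draw.
- Label the Week 12 ECG predose.
- State the intended timing, or that it is free, for early-discontinuation and extension ECGs.

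In Protocol Section 9.4.5 and SAP Section 5.6, summarise post-dose (Week 4) and trough (Week 12) QTcF change separately by arm.

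The sponsor should also reconcile, within Section 8.2.3, the single recordings with the mean QTcF and the post-dose timepoint. No threshold or stopping rule is proposed here.

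The cost is a footnote and a few sentences. Every participant already takes the Week 4 dose in clinic and stays, fasted, for the 1–2 h draw, so there is no extra ECG, visit or blood sample, and each Week 4 fenebrutinib tracing is paired with a PK sample. The downside is that the Week 4 ECG is recorded 1–2 h later in the day than baseline. The shift is the same in both arms, so the comparison with placebo accounts for it, but within-arm changes at Week 4 should be read with it in mind.
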